3.1.3. Data Safety Monitoring Board

An independent Data Safety Monitoring Board (DSMB), with expertise and experience in the pathology, and without direct involvement in the conduct of the trial, will be set up specifically to guarantee effective protection of subjects, insure the ethical conduct of the trial, benefit/risk ratio of the trial, and to ensure the independent review of the scientific results during the trial (every 4 patients recruited) and at the end of the trial.

The DSMB may recommend the early termination of the trial at any time if an unacceptable toxicity occurs.

The DSMB has only a consultative role; it will inform the sponsor who will decide whether the DSMB recommendation will be followed. A DSMB charter must be available upon submission of the trial (initial protocol) to the respective competent authorities.

3.2. Duration of study participation

From a subject standpoint, the study participation is defined as

- Two to four weeks of screening period;
- Four weeks (Cohorts 1 & 2) or twelve weeks (Cohort 3) as the treatment period (ABX464);
- Follow-up visits at 1 week and 4 weeks after cessation of study medication.

Overall, the minimal study duration will be approximately 70 days and up to 140 days depending on the subject Cohort.

4. STUDY POPULATION

4.1. Number of Subjects/Centers

36 Subjects will be enrolled in this study. These subjects will be enrolled at one site in Spain.

4.2. Eligibility Criteria

4.2.1. Inclusion Criteria

Subjects will be eligible for inclusion in this study only if ALL of the following criteria apply:

- Males aged 18-65 years;
- Subjects with hematological and biochemical laboratory parameters as follows and within 3 weeks of baseline:
 - Hemoglobin > 9.0 g/dL;
 - Absolute neutrophil count \geq 750/mm³;
 - Platelets \geq 100,000/mm³;
 - Total serum creatinine \leq 1.3 x ULN (upper limit of normal);
 - Creatinine clearance $>$ 50 mL/min by the Cockcroft-Gault equation within 60 days of entry;
 - Total serum bilirubin $<$ 1.5 xULN;
 - Alkaline phosphatase, AST (SGOT) and ALT (SGPT) $<$ 1.5 xULN;
 - Serum lipase less than or equal to 2.0 xULN;
- Subjects should be able and willing to comply with study visits and procedures as per protocol;
- Subjects should understand, sign and date the written voluntary informed consent form at the screening visit prior to any protocol-specific procedures being performed;
- Subjects must agree to use in addition to the condom, a second highly effective method (one for the subject and one for the partner) of contraception (defined as per the CTGF Guidance) during the study and for 3 months after end of study or early termination.

For HIV infected Subjects

- Subjects with a positive HIV-1 serology at any time before the study entry.
- Subjects treated for at least 12 months prior to screening with Dolutegravir or Raltegravir combined with either Tenofovir + Emtricitabine (TDF/FTC) or Abacavir + Lamivudine (ABC/3TC);
- Subjects with HIV plasma viral load \leq 50 copies/mL during the 6 months prior to screening with a maximum of 2 blips \leq 1000 copies during this period;
- Subjects' CD4+ T cells count \geq 250 cells per mm³ at any time since diagnosis;
- Subjects with CD4+ T cells count \geq 600 cells per mm³ at screening.

4.2.2. Exclusion Criteria

The following criteria should be checked at the time of screening. If ANY exclusion criterion applies, the individual will not be included in the study:

- History of allergic disease, anaphylaxis or reactions likely to be triggered or exacerbated by any component of the vaccine such as lactose;
- Acute or chronic infectious disease other than HIV infection (include but not limited to viral hepatitis such as hepatitis B, hepatitis C, active tuberculosis, active syphilis [i.e. currently untreated]).
- Acute, chronic or history of clinically relevant pulmonary, cardiovascular, gastrointestinal, hepatic, pancreatic or renal functional abnormality, encephalopathy, neuropathy or unstable CNS pathology, angina or cardiac arrhythmias, or any other clinically significant medical problems as determined by physical examination and/or laboratory screening tests and/or medical history;

- Severe hepatic impairment;
- Acute, chronic or history of immunodeficiency or autoimmune disease other than HIV infection;
- Unstable asthma (defined as sudden acute attacks occurring in less than three hours without an obvious trigger, hospitalization for asthma in the last two years); food or wine induced asthma;
- History of malignancy unless there has been surgical excision that is considered to have achieved cure;
- Active malignancy that may require chemotherapy or radiation therapy;
- Seizure disorder or any history of prior seizure;
- Serious illness requiring systemic treatment and/or hospitalization within 7 days prior to baseline;
- Active drug or alcohol abuse or dependence;
- Subjects reporting a use of a prohibited medication;
- History of significant gastrointestinal bleeding in the opinion of the investigator;
- Abnormalities of the colorectal mucosa, or significant symptom(s), which in the opinion of the clinician represents a contraindication to protocol-required biopsies (including but not limited to presence of any unresolved injury, infectious or inflammatory condition);
- Any condition, which in the opinion of the investigator, could compromise the subject's safety or adherence to the study protocol.

5. STUDY ASSESSMENTS AND PROCEDURES

5.1. Study Flow Chart

A detailed study flow chart (with all assessments) is displayed below.

Study procedures	Screening Visit	Baseline Visit	Control Visits	Day 28 / D56	End of Study treatment visit	FU visit	FuS visit Cohort 1&3	FuS visit Cohort 2
	Screening 21 ± 7 days	Baseline	Cohort 2 only ± 2 days	Cohort 3 only ± 2 days	28-Day (Cohort 1&2), 84-Day (Cohort 3) ± 2 days	FU visit 1-week post completion ± 2 days	FU visit 4 weeks post completion ± 7 days	FU visit 4 weeks post completion ± 7 days
Informed Consent	X	Day 1	Day 7, 14, 21	Day 28 / D56	Day 28 / Day 84	Day 35 / Day 91	Day 56 / Day 112	Day 56
Inclusion/Exclusion Criteria	X							
ECG	X	X			X		X	X
Adverse Event reporting	X	X	X	X	X	X	X	X
Concomitant medication checks and	X	X	X	X	X	X	X	X
Physical examination and vital signs	X	X	X	X	X	X	X	X
Hematology & Biochemistry	X	X						
Syphilis, HBV/HCV serology	X							
HIV-1 antibody serology #	X							
Urine and Rectal GC/CT (NAAT)	X				X	X	X	X
TNR & PT	X	Δ			Δ	Δ	Δ	Δ
HIV-1 viral load \$	X	X			X*	X	X	X
CD4+ and CD8+ counts \$	X	X			X*	X	X	X
Pharmacokinetics: Plasma and PBMC		0h, 0.5h, 1h, 1.5h, 2h, 4h, 6h and 8h	X*	X*	0h, 0.5h, 1h, 1.5h, 2h, 4h, 6h and 8h	X Trough	X Trough	X Trough
Flexible sigmoidoscopy for Rectal Biopsy		X			X*	X	X	X
- Explant infection #	X				X*	X	X	X
- MMC flow cytometry	X				X*	X	X	X
- Rectal microbiome	X				X*	X	X	X
- Rectal proteomics	X				X*	X	X	X
- Rectal transcriptomics	X				X*	X	X	X
- Rectal tissue pharmacokinetics	X				X*	X	X	X
- Rectal HIV Reservoir \$	X				X*	X	X	X
Blood samples for Immunology & Molecular assays		X			X*	X	X	X
- PBMC flow cytometry	X				X*	X	X	X
- Plasma SCAs \$	X				X*	X	X	X
- Plasma inflammatory markers	X				X*	X	X	X
Blood samples for HIV reservoir assays \$		X			X	X	X	X
- PBMC HIV reservoir \$	X				X	X	X	X

CT; Chlamydia trachomatis, GC; Neisseria gonorrhoea, HBV; hepatitis B virus, HCV; hepatitis C virus, INR; international normalized ratio, NAAT; nucleic acid amplification testing, MMC; mucosal mononuclear

5.2. Study Endpoints

- Primary endpoint:
Main pharmacokinetic parameters (Cmax, AUC) after first dose of ABX464 (Day 1):
 - Cohort 1: at Day 28 and at Day 56 for plasma, PBMC and rectal tissue.
 - Cohort 2: at Day 28 and at Day 56 for plasma and PBMC. Rectal tissue only at Day 28.
 - Cohort 3: at Day 28, Day 84 and Day 112 for plasma, PBMC and rectal tissue.
 -
- Secondary endpoints:
 - Number and grade of treatment-emergent adverse events, including treatment-emergent serious adverse events, adverse events leading to investigational product discontinuation, during the study;
 - Change in GALT HIV reservoirs in rectal tissue from Baseline to Day 28 and Day 56 in HIV-infected subjects (Cohort 1) and from Baseline to Day 28, Day 84 and Day 112 (Cohort 3);
 - Change in total viral DNA in the reservoir cells from Baseline to Day 28 and Day 56 in HIV-infected subjects (Cohort 1) and from Baseline to Day 28, Day 84 and Day 112 (Cohort 3);
 - Change in inflammatory markers in plasma from Baseline to Day 28 and Day 56 in subjects enrolled in Cohort 1 & 2 and to Day 28, Day 84 and Day 112 in subjects enrolled in Cohort 3;
 - Change in immunophenotype and assessment of cell-activation markers from Baseline in PBMCs and MMC, using an 11-colours panel, including: CD3, CD8, CD4, CD45RA, CCR7, CD27, CD28, CD38, HLA-DR, PD-1, viability to Day 28 and Day 56 in subjects enrolled in Cohort 1 & 2 and to Day 28, Day 84 and Day 112 in subjects enrolled in Cohort 3;
 - Change in HIV-1 RNA, CD4+ and CD8+ counts from Baseline to Day 28 and Day 56 in HIV-infected subjects (Cohort 1) and from Baseline to Day 28, Day 84 and Day 112 (Cohort 3);
 - Change of rectal microbiota using taxonomic markers from Baseline to Day 28 and Day 56 in subjects enrolled in Cohort 1, **change of rectal microbiota using taxonomic markers from Baseline to Day 28 in subjects enrolled in Cohort 2 and to Day 28, Day 84 and Day 112 in subjects enrolled in Cohort 3;**
 - Change in the transcriptome & proteome from Baseline to Day 28 and Day 56 in subjects enrolled in Cohort 1, **change in the transcriptome & proteome from Baseline to Day 28 in Cohort 2 and to Day 28, Day 84 and Day 112 in subjects enrolled in Cohort 3.**

5.3. Study conduct

It is the investigator's responsibility to ensure that all the assessments are carried out during each visit and that the intervals between visits/follow-ups are adhered to.

5.3.1. Screening Visit (21 ± 7 days prior to baseline)

The subjects will be informed about the general aspects of the study and will sign the screening informed consent form. The subject's number will be allocated once the subjects will be created in the eCRF. Only when consent has been given may further study procedures be carried out. During the screening phase, the following assessments will be performed:

- Signed informed consent form;
- Demographic data: date of birth; ethnicity;
- Medical history
- Physical examination and vital signs;
- Hematology (incl. INR and PT);
- Biochemistry;

- Serology (HIV, HBV, HCV, and syphilis) & Urine and Rectal GC/CTNAAT;
- Viral Load, CD4/CD8 count (HIV infected Subjects);
- 12 lead ECG;
- Concomitant medications.

5.3.2. Baseline Visit (Day 1)

- Physical examination and vital signs;
- Microbiome specimen collection (swabs);
- Hematology (incl. INR and PT if clinically indicated);
- Biochemistry;
- 12 lead ECG;
- Viral Load, CD4/CD8 count (HIV infected Subjects);
- Blood collection for HIV reservoir assessment (HIV infected Subjects) and immuno-evaluation;
- Flexible sigmoidoscopy with collection of rectal biopsies;
- Dispense study treatment to subject and instruct how to take them
- Perform PK blood samples (0h, 0.5h, 1h, 1.5h, 2h, 4h, 6h and 8 hours);
- Adverse event assessment.

5.3.3. Control Visits 3,4, & 5 (Days 7, 14, & 21)- Cohort 2

To be performed only in HIV-uninfected subjects:

- Physical examination and vital signs;
- Check Study treatment compliance;
- Adverse event assessment.

5.3.4. Day 28 Visit (\pm 2 days)- Cohort 3

To be performed only in subjects enrolled in the Cohort 3:

- Physical examination and vital signs;
- Microbiome specimen collection (swabs);
- Hematology (incl. INR and PT if clinically indicated);
- Biochemistry;
- Viral Load, CD4/CD8 count;
- Blood collection for HIV reservoir assessment and immuno-evaluation;
- Flexible sigmoidoscopy with collection of rectal biopsies;
- Perform PK blood samples (0h, 0.5h, 1h, 1.5h, 2h, 4h, 6h and 8 hours);
- Check Study treatment compliance;
- Adverse event assessment.

5.3.5. Day 56 Visit (\pm 2 days)- Cohort 3

To be performed only in subjects enrolled in the Cohort 3:

- Physical examination and vital signs;
- Hematology and Biochemistry;

- Blood collection for HIV reservoir assessment and immuno-evaluation;
- Check Study treatment compliance;
- Adverse event assessment.

5.3.6. End of study treatment visit (D28 for cohort 1&2 or D84 for cohort 3; \pm 2 days)

- Physical examination and vital signs;
- Microbiome specimen collection (swabs);
- Hematology (incl. INR and PT if clinically indicated);
- Biochemistry;
- 12 lead ECG;
- Viral Load, CD4/CD8 count (HIV infected Subjects);
- Blood collection for HIV reservoir assessment (HIV infected Subjects) and immuno-evaluation;
- Flexible sigmoidoscopy with collection of rectal biopsies;
- Perform PK blood samples (0h, 0.5h, 1h, 1.5h, 2h, 4h, 6h and 8 hours);
- Check Study treatment compliance;
- Adverse event assessment.

5.3.7. Follow-up Visit (D35 for cohort 1&2 or D91 for cohort 3; \pm 2 days)

- Physical examination and vital signs;
- Hematology (incl. INR and PT if clinically indicated);
- Biochemistry;
- Viral Load, CD4/CD8 count (HIV infected Subjects);
- Perform PK blood sample (at 9AM \pm 1hour);
- Adverse event assessment.

5.3.8. End of Study Visit (D56 for cohort 1&2 or D112 for cohort 3; \pm 7 days)

- Physical examination and vital signs;
- Microbiome specimen collection (swabs);
- Hematology (incl. INR and PT if clinically indicated);
- Biochemistry;
- Urine GC/CT NAAT & Rectal GC/CT NAAT;
- HIV serology (HIV uninfected participants)
- 12 lead ECG;
- Viral Load, CD4/CD8 count (HIV infected Subjects);
- Blood collection for HIV reservoir assessment (HIV infected Subjects) and immuno-evaluation;
- Flexible sigmoidoscopy with collection of rectal biopsies (Cohort 1 and 3 only)
- Perform PK blood sample (at 9AM \pm 1hour);
- Adverse event assessment.

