5.4. Detail of the study assessments

5.4.1. Physical Examination and Vital Signs

A routine physical examination (including body weight) will be done at each study visit. Physical examination at baseline will cover eyes, ears, nose, throat, lungs/thorax, heart/cardiovascular system, abdomen, skin and mucosae, nervous system, lymph nodes, musculoskeletal system, and, if applicable, others. At follow up, physical exams will be symptom directed. Any new clinically relevant finding compared to baseline must be documented as adverse event.

Measurements of vital signs will be done at each visit (Blood pressure, Heart Rate, Body temperature). The subject should rest for at least 15 minutes prior to measurements. The measurements can be performed either in sitting or supine position of the subject. The right or left arm may be used. However, the position and the arm used for measurement should be kept constant throughout the trial for an individual subject.

The investigator should ensure that each parameter outside the normal range is assessed for clinical significance. For any deviation assessed clinically significant, the investigator has to document the change as an AE in the CRF.

In addition, it is at the discretion of the investigator to document any change or trend over time in vital signs as an AE if he considers the change to be clinically significant, even if the absolute value is within the alert limit or reference range.

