7. SUBJECT COMPLETION AND WITHDRAWAL

7.1. Subject Completion

Treatment with ABX464 shall continue until Day 28 (Cohort 1&2) or Day 84 (Cohort 3), except if a subject fulfils a premature discontinuation criterion (defined below). After discontinuation of study product (End of Rx Visit; Day 28/84) subjects will return for two follow-up visits (FU Visit; Day 35/91 and EoS Visit; Day 56/112).

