9.3. Safety Analyses

Adverse events will be coded using the standard dictionary (MedDRA) down to the lower level term (LLT).

An overall summary table will be presented: any adverse event, any treatment emergent adverse event (TEAE), any serious adverse event (SAE), death, any grade 3 or higher adverse events from baseline to EoS.

Two periods will be defined for TEAE:

- Any adverse event which occurs or worsens from first dosing to Day 28;
- Any adverse event which occurs after Day 28.

Adverse events will be described by primary system organ class and preferred term. Numbers and percentage of subjects, and number of occurrence of adverse event will be presented for:

- TEAE;
- Serious TEAE;
- TEAE leading to drug discontinuation;
- TEAE of grade 3 or 4;
- TEAE for which relationship with the study drug is recorded as possible or probable.

The assessment of safety will be based on the frequency of adverse events (with and without regard to causality) graded according to the Division of AIDS table for grading the severity of adult and pediatric adverse events (version 2.0, November 2014) and also, the review of individual values for clinical laboratory data, vital signs and ECG focusing on the detection of abnormal values and PCSAs [potentially clinically significant abnormalities (PCSA) determined upon investigator considerations].

Adverse events will be tabulated (counts and percents) by group. All adverse events will be listed and the data will be tabulated by body system/organ class. Adverse event tabulations will include all treatment emergent adverse events, which will be further classified by severity, and relationship to treatment and dose level.

Clinical laboratory parameters, vital signs, ECG will be summarized by using descriptive statistics (n, mean, SD, SEM, median, minimum and maximum). Number of subjects with at least one abnormal values will be tabulated (counts and percents) for each parameter in summary shift tables, by group and dose.

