## 9 Data

## 10 Statistical Methods

### 10.1 General Principles

All statistical methods will be based on the International Conference on Harmonisation (ICH) E9 document "Statistical Principles for Clinical Trials".

Data will be summarised by cohort. A total column showing all patients will be included for baseline and safety summaries. Where appropriate, data will also be summarised by visit with summaries for each visit attended as scheduled and an additional summary for final (last scheduled visit or early withdrawal). The format of the summaries is defined in the shells in a separate document.

All summary tables will be made up of the following three columns:

- Cohort 1: Hiv infected subjects receiving the 150mg dose of ABX464 for 28 days;
- Cohort 2: Hiv uninfected subjects receiving the 50mg dose of ABX464 for 28 days;
- Cohort 3: Hiv infected subjects receiving the 50mg dose of ABX464 for 84 days.

In addition, summary tables for total DNA will be made up with an additional column of cohort 1 and Cohort 3 pooled.

In summary and analysis tables of continuous variables, standard descriptive statistics (N, mean, standard deviation [SD], median, quartiles, minimum, maximum ) will be presented when relevant. 95% confidence Intervals (CI) will be presented in the statistical analysis outputs as appropriate. For PK summaries, arithmetic mean (AM), geometric mean (GM) and coefficient of variation (%CV) will be used to summarise the data. The minimum and maximum statistics will be presented in summary tables to the same number of significant figures as the original data. The mean/AM, median, GM, CI, SD and will be presented to one more significant than the original data.

For numeric data which includes non-numeric values (e.g. PK data reported as BLQ or lab results reported as < 10 or >100) the following principles will be applied when summarising the data:

- BLQ will be replaced with a value that is ½ of the lower limit of quantification (LLQ)
- Results reported as < x will be treated in the same way as BLQ with LLQ=x
- Otherwise AM, GM, SD, CI and %CV will not be calculated
- Whenever meaningful, minimum, median and maximum will be presented based on the reported data (e.g. minimum = <10, median = 20, maximum = >100)

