### 11.4.1 Adverse Events

All adverse events (AE) will be classified using the version of the MedDRA coding dictionary.

Events will be classified as treatment-emergent if they started or increased in severity on or after the first date and time of medication dosing at Day 1 and up to End of Rx, or withdrawal date if the

patient discontinues before End of Rx. If an event start date is partial, then the start day, month, year or stop date will be used to determine if the event is treatment-emergent. If the classification of the AE cannot be determined from the data available, then the event will be considered treatment-emergent.

Any adverse event which occurs after End of Rx will be classified as post-treatment-emergent.

An overall summary table will be presented using the safety set for adverse events occurring from baseline to the end of the study in the following categories:

- Any adverse event;
- Any treatment-emergent adverse event (TEAE);
- Any post-treatment-emergent adverse event;
- Any serious adverse event;
- Any severe adverse event (Common Toxicity Criteria [CTC] grade 3 or 4);
- Death

TEAEs will be further classified and summarised as follows:

**Severe TEAEs:** Severity classified as 'Grade 3', 'Grade 4' or missing.

**Serious TEAEs:** Seriousness classified as 'yes' or missing.

**Drug-related TEAEs:** Relationship to study drug classified as 'yes' or missing.

**Serious drug-related TEAEs:** Both serious and drug-related, as specified above.

**TEAEs leading to study drug discontinuation:** Action taken classified as 'permanent discontinuation'.

Summaries by system organ class (SOC) and preferred term (PT) will also be presented for treatment-emergent events. Similar tables will be presented for each of the classifications of treatment-emergent events above.

A summary of the mean duration (days) of treatment-emergent events will also be presented by SOC and PT, along with the number of events. Duration of an event is calculated as (stop date of event - start date of event) + 1. If an AE is ongoing then use the end of study date (or last known visit date for early termination) as the stop date.

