All AE summary tables, unless otherwise specified, will show the number (%) of patients having at least one event and the number of events in each treatment group and overall. Note: If a patient has multiple AEs with the same preferred term, these will be summarised once within the count for N (%) of patients, but each event will be counted within the number of reports E of each AE. Changes in severity of the same AE (if collected) will be counted only once within the number of reports E of each AE.

All adverse events recorded on the CRF will be listed by SOC and PT within the data listings.

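### SAP 11.4.1 counts TEAEs over 28, 28 and 84 days in Cohorts 1, 2 and 3, and its text does not carry over the common Day 28 period defined in Protocol 9.3

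*Protocol*

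**What the plan says.** **Window.** SAP 11.4.1 classes an event as treatment-emergent if it began or became more severe on or after "the first date and time of medication dosing at Day 1 and up to End of Rx" (or withdrawal, if earlier). Anything later is post-treatment-emergent. End of Rx is Day 28 in Cohorts 1 and 2 and Day 84 in Cohort 3 (Protocol 7.1; SAP 3.4). Protocol 9.3 instead splits TEAEs at Day 28, with no restriction by cohort. Its first period is "Any adverse event which occurs or worsens from first dosing to Day 28", and its second is everything after Day 28.

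**Presentation.** SAP 10.1 puts the three cohorts in adjacent columns and adds: "A total column showing all patients will be included for baseline and safety summaries". SAP 11.4.1 says that the AE tables "will show the number (%) of patients having at least one event and the number of events in each treatment group and overall". SAP 10.1 also notes: "The format of the summaries is defined in the shells in a separate document".

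**Contacts.** Protocol 5.3.3 schedules control visits on Days 7, 14 and 21 with an examination, vital signs and an AE assessment, "To be performed only in HIV-uninfected subjects". Protocol 8.5 has subjects asked about AEs at study visits. Protocol 5.4.1 adds: "Any new clinically relevant finding compared to baseline must be documented as adverse event". The same section makes follow-up examinations symptom directed. Protocol 6.3.1 gives every subject a diary that can record side effects.

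**The concern.** Safety is the first-listed secondary objective, and descriptive tables are its whole output. A reader will naturally look across the columns. The 50 mg HIV-infected column is counted for 84 days and stands beside a 150 mg HIV-infected column counted for 28. If events keep arising after Day 28, the lower dose can show as many patients with a TEAE as the higher dose, or more, only because it was watched for longer. Event counts are affected in the same way, and the total column adds the two windows together. A reader can see that the durations differ, but cannot recover a Day 28 count from an 84-day table.

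The contact schedule raises a separate, smaller question. Cohort 2 is asked about AEs more often in its first four weeks, so mild transient events may be recorded somewhat more fully there.

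**Working it through.** The plan gives no expected AE rate and no sample size calculation, so there is no figure to reproduce. The schedule facts below come from the documents. The incidences and hazards are assumptions.

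**1. Window and exposure.** The nominal windows are 28, 28 and 84 days; 84/28 = 3. Planned treatment days are 12 × 28 = 336 in each of Cohorts 1 and 2, and 12 × 84 = 1008 in Cohort 3, in total 1680. Cohort 3 supplies 1008/1680 = 60% of the days behind the total column. With a cut at Day 28 it would supply one third.

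**2. Patients with at least one TEAE.** Assume the same true 28-day incidence p28 in every cohort. Let f be the hazard after Day 28 divided by the hazard before. Days 29 to 84 are two further 28-day blocks, so

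p84 = 1 − (1 − p28)^(1 + 2f)

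| p28 | Cohort 1, of 12 | Cohort 3, of 12 (f = 1) | Ratio, f = 1 | Ratio, f = 0.25 | Ratio, f = 0 |
|---|---|---|---|---|---|
| 25% | 3 | 6.9 (p84 = 0.578) | 2.31 | 1.40 | 1.00 |
| 50% | 6 | 10.5 (p84 = 0.875) | 1.75 | 1.29 | 1.00 |
| 75% | 9 | 11.8 (p84 = 0.984) | 1.31 | 1.17 | 1.00 |

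For rarer events the constant-hazard ratio is larger but rests on few patients. At p28 = 10%, p84 = 27%, or 1.2 against 3.3 of 12.

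**3. Variation between subjects.** Step 2 gives every subject the same hazard. If the 28-day risk varies, with f = 1, then p84 = 1 − E[(1 − p)^3]:
- Beta(1,3), mean 25%: 1 − 0.50 = 0.50, ratio 2.00.
- Uniform, mean 50%: 1 − 0.25 = 0.75, ratio 1.50.
- Beta(3,1), mean 75%: 1 − 0.05 = 0.95, ratio 1.27.

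So, at a given incidence, the f = 1 column in step 2 is the upper end.

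**4. Number of events.** On the same assumptions the expected event count in Cohort 3 relative to Cohort 1 is 1 + 2f: 3.0, 1.5 and 1.0 for f = 1, 0.25 and 0.

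**5. Total column.** With f = 1, 24 × p28 + 12 × p84 gives 12.9, 22.5 and 29.8 of 36. Cut at Day 28, it gives 9, 18 and 27.

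**6. Contacts.** From Protocol 5.3.2 to 5.3.6, scheduled AE assessments after Day 1 up to Day 28 are:
- Cohort 1: Day 28 (one).
- Cohort 2: Days 7, 14, 21 and 28 (four).
- Cohort 3: Day 28 (one).

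The longest nominal gap is 7 days in Cohort 2 and 27 days in the other two. The documents give nothing from which to compute the effect on AE counts.

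**7. After a Day 28 cut.** Windows become 28, 28 and 28 days. Contacts stay at 1, 4 and 1.

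**The case against.** Several points on the other side stand.

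- **Duration is not hidden.** SAP 10.1 defines the columns by dose and treatment length, and SAP 11.5 summarises exposure in days and doses given. This tells the reader that the windows differ; it does not equalise them.
- **The shells may already hold a Day 28 table.** They were not available, so only the SAP text can be faulted. Onset dates are collected and all AEs are listed, so no information is lost.
- **End of Rx is a sound on-treatment definition.** It should stay. The gap is the missing common period beside it.
- **No cross-cohort comparison is planned.** The safety objective is to describe ABX464 alone in uninfected subjects and with antiretrovirals in infected subjects. There is no test and no decision rule. With 12 per cohort, chance is large anyway: 6 of 12 has an exact 95% interval of 21% to 79%.
- **The inflation may be nil.** It vanishes if no new AEs arise after Day 28.

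A reader might infer that the plan biases a dose comparison. The documents do not support that: the cohorts are sequential, open-label and not randomised, and no dose contrast is specified. A reader might also infer that the extra visits materially inflate AEs in Cohort 2. That goes too far as well. Follow-up examinations are symptom directed, every subject has a diary for symptoms, and the size of any effect is unknown. What remains is a caution.

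**Conclusion.** The point holds as a gap between the SAP text and Protocol 9.3. Followed as written, SAP 11.4.1 shows Cohort 3 over three times the window of the other cohorts and mixes the windows in the total column. The effect on patients with at least one TEAE, Cohort 3 against Cohort 1, runs from 1.0 to about 2.3 for a 28-day incidence of 25% to 75%. It depends on the hazard after Day 28 and on variation between subjects. The upper figure assumes a constant hazard that is the same in every subject and cohort; the lower assumes no new events after Day 28. The harm is limited to misreading descriptive tables. The difference in contacts is real but minor. Low severity; a cheap improvement.

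**What to change.** Amend SAP 11.4.1 before database lock:

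1. Keep the End of Rx tables.
2. Add one TEAE summary, for all three cohorts and the total column, of events that started or worsened from first dose to Study Day 28 (or withdrawal, if earlier), the period in Protocol 9.3. If the shells already contain it, one sentence in the SAP is enough.
3. In that table, show the grade reached by Day 28 only where severity changes were recorded with dates. Protocol 8.5 does not list a date of severity change, SAP 11.4.1 treats such changes as possibly not collected, and SAP 10.1 collapses them to the maximum. Otherwise show the recorded grade, and footnote that it may reflect later worsening.
4. Footnote that scheduled AE assessments after Day 1 up to Day 28 number 1, 4 and 1, so all-grade Cohort 2 counts should be compared with caution.

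The cost is one table and its footnotes, with no new visits or data. The table corrects the window only; the footnote discloses the contact difference without correcting it. One limit remains: early events can still be reported late, at Day 35 in Cohort 1 but not until Day 56 in Cohort 3.
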